## **Interventions and Interactions**

*The essential features of interventions and interactions used to generate data for the study should be described.*

- **Intervention:** Periodic (every 8 weeks) phlebotomy of 500 mL (one “Unit”) sufficient to reduce serum ferritin from the upper half of normal to the lowest 20% of normal (Males 20-40, Females 20-40 ng/ml) (35). In our pilot study, subjects reached similar ferritin levels with donation of  $3.4 \pm 0.5$  Units. In that case subjects donated one Unit per month and there were no adverse events; that interval has been increased in this study to 8 weeks to conform to current Red Cross practices.
- **Sham Phlebotomy:** As any other study, interventions are subject to placebo effects, and the same is true for phlebotomy. We are thus including a sham phlebotomy as described in the procedures, below.
- **Study Protocol.** The inclusion and exclusion criteria are listed in **3.A**. We are including arms to address prediabetes and diabetes separately because there is the possibility that the former will respond more robustly to therapy because they will not have had the disease long enough to develop a significant degree of insulin deficiency, a feature of T2DM that may be difficult to reverse in middle-aged or older adults. Our small pilot trial showed improvement in both groups, but 2/3 of those with prediabetes reverted to normal glucose tolerance, a surprisingly good result. For the reason of reversibility cited above, we are not including anyone on insulin; furthermore, anyone on insulin or other agents with the potential to cause hypoglycemia are also excluded because if their insulin sensitivity improves with iron reduction, as the Preliminary Data suggest, they could be more prone to hypoglycemia.

Serum ferritin will be used as the primary assessment of tissue iron stores. It is an excellent and reliable marker of tissue iron, even in those with significant comorbidities including advanced NASH (26). There is an inflammatory component to obesity and T2D, and hence there is a small increase in ferritin with obesity noted in some but not all studies (e.g. Fig. 3 in (36)). However, the magnitude of the average difference with obesity (~20 ng/ml) is tiny, 7% compared to the normal range in the population (20~300 ng/mL). The paper showing the largest difference with obesity is only true when the compared to BMI <25, whereas there is no change at all going from the group with BMI of 25-30 (ave. ferritin 144), to 30-35, 35-40, and >40 (ave. ferritin 146)! (37). NHANES data show that people with diabetes and high-ferritin are heavier consumers of red meat, and ferritin is not accounted for by markers of inflammation (7), confirmed in a more recent study (38). We showed no relation of CRP to ferritin in obese T2D (20). That ferritin is overwhelmingly reporting iron status rather than inflammation is also backed by biopsy-based studies in NASH (29). In every subject in our pilot, ferritin fell uniformly and promptly with phlebotomy, which would not happen if ferritin were mainly reporting inflammation. To the degree that obesity *per se* contributes to ferritin, it is overwhelmed by the contribution of iron. We will further exclude the possibility that it may be falsely reporting inflammatory stress by excluding individuals with elevation of the inflammatory marker C-reactive protein. A second measure of tissue iron, serum “soluble transferrin receptor,” will be obtained as confirmation of the assessment of ferritin, but not used for inclusion/exclusion because it is less well-validated.

- **Study Procedures: Basic Study.** These are summarized in the accompanying table.

	Screening (Not fasting)	Visit 1 (not fasting)	Visit 2 (fasting)	Visit 3 (not fasting)	Visit 4 (Not fasting)	Visit 5 (not fasting)	Visit 6 (not Fasting)	EOS 1 (fasting)	EOS 2 (fasting)
Consent	X								
Inclusion/Exclusion	X								
Medical History	X								
Review Medications	X		X	X	X	X	X	X	
Vital Signs (following BP protocol)	X		X	X	X	X	X	X	X
Physical Exam	X							X	X
Adverse Events	X		X	X	X	X	X	X	X
CGM Placement		X						X (returned by mail)	X (returned by mail)
Return CGM and Download Data			X						
Hemoglobin-WFU CRU	X		X	X	X	X	X	X	X
Ferritin, serum	X (if not available)		X	X	X	X	X	X	X
HgbA1c	X (if not available)							X	X
CRP	X							X	X
Insulin (fasting)			X					X	X
Lipid panel (fasting)			X					X	X
CMP (14)			X					X	X
CBC platelets no Diff	X							X	X
*Fibroscan			*X					*X	*X
Blood for Research Storage (to be sent to Wake Forest)	X		X	X	X	X	X	X	X
Phlebotomy Procedure (including all vital sign measurements prior and post procedure) Phlebotomy De-identified Discarded samples sent to the Olin Physical Lab – WFBH site only			X	X	X	X	X		

\* –Fibroscan at WFBH site only

- a. Screening Visit (Not fasting):** Consent, assessment of inclusion/exclusion criteria, serum ferritin (if not available within last year), CBC, Platelets, no differential, C-Reactive Protein (CRP), Hemoglobin, and HgbA1C (if not available through the electronic health record in the last 3 months). Subjects will be counseled to reduce weight if they are overweight or obese, using the protocol of the Diabetes Prevention Program (39). Subjects who complete the screening visit will be compensated \$100 for their time.
  - a.1 Rescreening: Due to the COVID-19 pandemic delay in research visits, any subject that was previously screened but was not able to initiate the study can be rescreened; if eligible all subsequent visit will proceed in accordance with the protocol.
- b. Visit 1 (not fasting) (~30 min):** Placement of continuous blood glucose monitor (CGM). This is a small waterproof “pod” with a subcutaneous probe that provides a continuous record of glucose levels (every 5 min) for a period of 6-10 days. We will use the Abbott Libre that is FDA approved for monitoring glucose in patients with diabetes. This will provide more information than a single fasting glucose, an important consideration because of the variability of fasting glucose and the additional information provided regarding postprandial and nighttime levels. An added advantage is that after the initial placement and removal, when the subjects have gained familiarity with it, the device can be returned by mail back after the monitoring period. Subjects who complete Visit 1 will be compensated \$50 for their time.
- c. Visit 2 (7-14 days) (fasting) (~1 hr):** Report to the Clinical Research Unit (CRU) at University of North Carolina at Chapel Hill (UNC) or Wake Forest (WF) School of Medicine. Review Adverse Events (AE's). Measure outcome variables (weight, blood pressure; blood for, insulin, lipid panel, CMP (14), Ferritin) and the Ultrasound Fibroscan (WFBH site only). Subjects who complete Visit 2 will be compensated \$50 for their time.

*Randomization* (1:1) to control (sham phlebotomy) or phlebotomy groups with final target ferritin levels of 20-40 ng/ml for males and 20-40 for females. Phlebotomy will not be performed if hemoglobin is lower than 12.5 g/dL for women and 13.0 g/dL for men; in that case, subjects will undergo repeat hemoglobin measurement every 2 months. If the hemoglobin value increases above the threshold for phlebotomy at Visits 3 or 4, phlebotomy will be performed; otherwise, participants will have an “end of study” visit 1 at six months. If blood pressure declines by > 20 mm Hg systolic, or pulse increases by > 30 bpm upon standing, phlebotomy will not proceed.

*Phlebotomy:* Both groups will have a sleep mask-style blindfold placed or a barrier (e.g. a towel) will be placed between all subjects and the phlebotomy bag in order to prevent the subject from knowing if blood was drawn, and have a phlebotomy needle placed, usually in an antecubital vein. The treatment group will have 1 Unit (~500 mL) of blood removed, while in the placebo group the needle will remain clamped. After the usual 8-10 minutes required for removal of the unit, both groups will have the needle removed, be given a zero-calorie rehydration drink (12 oz) and remain seated for at least 5 min or until comfortable to stand. A snack will be offered. Blood pressure will be monitored after the procedure and if there is hypotension by the above criteria (see *Randomization*), the subject will be asked to remain another 5-10 min and encouraged to finish the drink or have a second. The phlebotomies or sham phlebotomies will be performed by research nurses in the CRU, who have the training and support to respond to a medical emergency. For considerations related to phlebotomy safety and the use of the placebo group, please refer Visit 3. *WFBH participants only:* The discarded phlebotomy blood will be de-identified and will be picked up by a representative from the [name], the sample will be stored in the Olin Physical Lab on the Reynolda campus, room 216. The blood will be used for in vitro experiments aiming to prevent thrombosis in extracorporeal circulation devices. An Institutional Review Board (IRB) must also approve any future research study using your blood sample.

*Review of laboratory findings:* Ferritin results will not be routinely available prior to phlebotomy, but will be reviewed 1-3 days after the visit. Once the serum ferritin results reach the target range (20-40 ng/ml), the subject will be moved to the End of Study sequence.

- **d. Visit 3 (8 weeks after Visit 2) (not fasting) (~1 hr.):** Review AE's. Draw blood for ferritin and perform on site determination of hemoglobin. If hemoglobin is lower than 12.5 g/dL for women and 13.0 g/dL for men, phlebotomy will not be performed and subject will be scheduled 8 weeks out for Visit 4. If the serum ferritin results from this visit have reached the target range (20-40 ng/ml), the subject will be moved to the End of Study sequence. If not, the subject will continue to Visit 4. Subjects who complete Visit 3 will be compensated \$50 for their time.
- **e. Visit 4 (not fasting):** Review AE's. Draw blood for ferritin and perform on site determination of hemoglobin. If hemoglobin is lower than 12.5 g/dL for women and 13.0 g/dL for men, phlebotomy will not be performed and subject will be scheduled 8 weeks out for Visit 5. At this visit, after the sham phlebotomy, all of the Placebo Group will be scheduled to the “end of study” sequence. Three phlebotomies were the average needed for the treatment group in the pilot study to achieve goal ferritin. If serum ferritin results of the treatment group subjects from this visit have reached the target range (20-40 ng/ml), the subject will be moved to the End of Study sequence. If not, the subject will continue to Visit 5. Subjects who complete Visit 4 will be compensated \$50 for their time.
- **f. Visits 5-6, if needed (not fasting):** Hemoglobin and Ferritin will be drawn. If hemoglobin is lower than 12.5 g/dL for women and 13.0 g/dL for men, phlebotomy will not be performed and subject will be scheduled 6 months out to start the End of Study sequence. If the serum ferritin results from Visit 5 have reached the target range (20-40 ng/ml), the subject will be moved to the End of Study sequence. If not, the subject will continue to Visit 6. After Visit 6, all subjects, regardless of serum ferritin results, will move to the End of Study sequence. Subjects who complete these visits will be compensated \$50 for their time per visit.
- **g. End of Study Visit 1 (6 months ± 2 weeks after last phlebotomy visit) (fasting) (~1 hr.):** Patient should come in fasting. Review AE's. Perform outcome measures (blood pressure, weight, CMP (14), CBC platelets no diff., insulin, HgbA1C, CRP, lipid panel, ferritin. Fibroscan (WFBH site only), place CGM, which the subject will mail back in a prepaid mailer. Subjects who complete this visit will be compensated \$100 for their time.

- **h. End of Study Visit 2 (6 months  $\pm$  2 weeks after E.O.S. 2) (fasting) (~1 hr.):** Patient should come in fasting. Review AE's. Perform outcome measures (CGM placement, blood pressure, weight, CMP (14), CBC platelets no diff., insulin, lipid panel, HgbA1C, ferritin, CRP, Fibroscan (WFBH site only)). Place CGM, which the subject will mail back in a prepaid mailer. Subjects who complete this visit will be compensated \$100 for their time.

- Study procedure: Liver Substudy
- The Screening Visit and Visit 1 will be the same as the Basic Study
- In addition to the other studies planned Visit 2 of the Basic Study, those in the Liver Substudy will have: Magnetic Resonance Imaging (MRI), FIBROSCAN done at Visit 2.
- Both Control and Treatment Groups will have an Ultrasound Fibroscan, the Fibroscan is a noninvasive imaging study that evaluates the degree of liver stiffness, which is a measure of the scarring or fibrosis that can occur with diabetes or fatty liver. It does this by determining the speed of sound waves through the liver utilizing a sonogram. The Magnetic Resonance Imaging (MRI) is a test that uses powerful magnets, and a computer to make detailed pictures inside your body. Neither test uses radiation.
- Following Visit 2, the RANDOMIZATION, PHLEBOTOMY, and END OF STUDY (E.O.S.) visits will occur just as in the Basic Study, the End of Study 1 will repeat the Fibroscan and End of Study 2 will repeat the Fibroscan and MRI.

- **Liver Substudy Calendar:** includes all main requirements with the addition of the Fibroscan and MRI

Procedure	Screening Visit (Not Fasting)	Month 0		Months 2-8 (as needed)			Month 11-12	Month 17-18
		Visit 1 (Not fasting)	Visit 2 (Fasting)	Visit 3 (Not Fasting)	Visit 4 (Not Fasting)	Visit 5, 6, ect. (Not fasting)	E.O.S. 1 (Fasting)	E.O.S. 2 (Fasting)
*Fibroscan			X				*X	*X
*MRI			**X					**X

\* – Fibroscan (additional test for Liver substudy)

\*\* - MRI

- Study procedures: Glucose Tolerance Mechanism substudy
- The Screening Visit and Visit 1 will be the same as the Basic Study.
- In addition to the other studies planned at Visit 2 those in the Glucose Tolerance Mechanism Substudy will have a Frequent Sample Intravenous Glucose Tolerance Test (FSIVGTT) at Visit 2.
- Both Control and Treatment Groups will have a glucose test that uses an IV it is called a Frequent Sample Intravenous Glucose Tolerance Test (FSIVGTT). There will be a plastic catheter (IV) placed in a vein in your arm and blood samples will be taken. A second IV will be placed in your other arm and dextrose (sugar water) will be given through that IV. For this test, you will be given 300mg/kg (or an average total of 20 grams) of glucose IV over one minute with bloods for insulin and glucose determination collected at one minute intervals for 6 minutes, then at two minute intervals until 18 minutes. At 20 minutes, you will be given 0.04 Unites/kg or regular insulin, or an average of 2-3 Units total. Samples of blood will continue to be taken until a total of 180 minutes have elapsed. This amount of insulin is much less, than your own body will be making in response to the glucose we gave you.

- During this visit, the total amount of blood taken from you will be approximately  $\frac{3}{4}$  cup (10 tablespoons). When your tests are completed, you will be given a snack and meal voucher.
- Following Visit 2, the RANDOMIZATION, Phlebotomy, and END OF STUDY (E.O.S.) visits will occur just as in the Basic Study, with the addition of the FSIVGTT at E.O.S 1 and E.O.S. 2.
- Glucose Tolerance Mechanism Substudy Calendar: includes all Main requirements with the addition of the FSIVTT test

Procedure	Screening Visit (Not Fasting)	Month 0		Months 2-8 (as needed)			Month 11- 12	Month 17- 18
		Visit 1 (Not Fasting)	Visit 2 (Fasting)	Visit 3 (Not Fasting)	Visit 4 (Not Fasting)	Visit 5, 6, ect (Not Fasting).	E.O.S. 1 (Fasting)	E.O.S. 2 (Fasting)
FSIVGTT			**X				**X	**X
*Fibroscan			*X				*X	*X

\*\* – Frequent Sample Intravenous Glucose Tolerance Test (FSIVGTT)

\* – Fibroscan

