### **Subjects selection criteria**

Subjects will have type 2 diabetes mellitus, or prediabetes, defined by HgbA1C criteria.

- **Inclusion Criteria.** Ages 40-75; At least 3 months since diagnosis of prediabetes or diabetes; HgbA1C value within three months or at screening of 5.7-6.4% for those with prediabetes, undiagnosed on no medication HgbA1C 6.5-6.9 and 7-8.5% for those with diabetes (the upper limit of the latter to reduce the likelihood of major changes in glycemic intervention during the trial period, and the lower limit to allow some room for improvement); Serum ferritin levels within 1 year or at the time of screening in the upper half of the normal range (>50 ng/mL for women and >100 ng/mL for men). C-reactive protein levels up to 11.0. Subjects will be on stable lifestyle therapy and 0-2 antihyperglycemic agents that are non-hypoglycemic (i.e. no sulfonylureas, glinides or insulin) to limit the chances of hypoglycemia if, as hypothesized, participants become more insulin sensitive with iron reduction. Aim 2 – serum ALT> 1.5 times the upper limit of normal, or; liver stiffness of > 12.5 kPa by Fibroscan transient elastography.
- **Exclusion Criteria.** Documented current anemia, hemoglobin levels within 0.5 g/dL of the lower limit of normal (<12.5 g/dL for women and 13.5 g/dL for men), or recent blood loss; bleeding diatheses (coagulation abnormalities or treatment with anticoagulants); serious chronic infections or chronic inflammatory conditions that could elevate ferritin as an "acute phase reactant;" C-reactive protein greater than 10.0, the upper limit of normal, to further validate the lack of significant chronic inflammation; active cancer diagnosis (excluding skin cell cancers other than melanoma); renal insufficiency (eGFR<60 ml/min); history of orthostatic hypotension; heavy alcohol use (NIH criteria, for men greater than 4 drinks on any day or 14/week, for women >3 drinks on any day or > 7/ week); pregnancy or premenopausal women of childbearing age, unless unable to become pregnant because of oral contraceptive use, IUD, birth control implants, surgical loss of ovaries or uterus. Aim 2 – individuals meeting the additional inclusion criteria for aim 2 will be tested for anti-HAV IgM, HBs Ag, anti-HBc. IgM, anti HCV IgM and IgG. Subjects who prove positive for any of these viral serologies, except for HCV IgG will be excluded. The latter will be tested for HCV RNA by PRC, and if negative they will be eligible for enrollment

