### **Analytical Plan**

#### **Statistical Plan and Data Analysis.**

The primary analysis will be an analysis of covariance to compare the mean change in the primary endpoint for each aim (HgbA1C at 6 months after phlebotomy for Aim 1, serum ALT at 12 months after phlebotomy for Aim 2, and DI at 6 months after phlebotomy for Aim 3) between the iron depletion and control groups in the full cohort of patients after controlling for the baseline levels of those measurements. The baseline HgbA1C is included as a covariate to increase study power by accounting for regression to the mean between the two time points.

*Secondary Analyses.* The effects of iron depletion on secondary continuous outcomes will be evaluated using analysis of covariance with adjustment for the baseline level of the factor being analyzed as well as the baseline HgbA1C level. For example, we will determine the degree of response (e.g. change in average glucose by CGM) as a function of starting ferritin, ending ferritin, and change in ferritin for determination of dose-response relationships. Treatment effects on dichotomous outcomes (e.g., conversion of pre-diabetes to diabetes) will be evaluated by exact logistic regression, controlling again for the baseline level of the analyzed factor. Ordinal logistic regression will be applied to compare categorical variables with more than 2 ordered categories. In expanded models, interaction terms between the treatment assignment and baseline HgbA1C level will be added to evaluate if the treatment effect differs across the HgbA1C range, and, in particular, between the diabetic and pre-diabetic patients in the study.

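### No HbA1c is drawn at Visit 2 and no baseline is defined, so the covariate in the primary ANCOVA can be a chart value more than three months old at randomisation

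*Combined protocol and SAP*

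**What the plan says.** In the procedures table (Study Procedures: Basic Study), HbA1c has three entries: screening (only if not already available), End of Study (EOS) 1 and EOS 2. The Screening Visit text lists "HgbA1C (if not available through the electronic health record in the last 3 months"). Eligibility uses the same window: "HgbA1C value within three months or at screening of 5.7-6.4% for those with prediabetes" (Subjects selection criteria).

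The instruction for Visit 2 is "Measure outcome variables (weight, blood pressure; blood for, insulin, lipid panel, CMP (14), Ferritin"). HbA1c is not in the list. Randomisation and the first procedure take place at this visit. Ferritin is handled differently: it too may be skipped at screening if a value exists, but the table then has it measured at Visit 2 for everyone.

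The Statistical Plan compares mean change in HbA1c between arms "after controlling for the baseline levels of those measurements" and gives the reason: "The baseline HgbA1C is included as a covariate to increase study power by accounting for regression to the mean between the two time points". Neither it nor any other section identifies the baseline value. At screening there is also this: "Subjects will be counseled to reduce weight if they are overweight or obese".

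**The concern.** The primary endpoint is the one main outcome without a baseline that the protocol itself measures at the visit of randomisation. Followed as written, the schedule gives some participants a study value from screening and others a chart value taken up to three months before screening. Visits 1 and 2 come after that, so the chart value can be older still at randomisation. For every participant the baseline is also the value that decided eligibility, which makes some regression to the mean likely.

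Three things are at stake. First, a less contemporaneous covariate predicts follow-up less well, so the ANCOVA gains less than it could. Second, the Sample Size and Statistical Power sections rest on within-subject change, and the secondary endpoints include conversion from prediabetes by HbA1c criteria. Neither within-subject change nor the baseline category is shielded from drift or selection error as the randomised contrast is. Third, the gap closes for good at the first phlebotomy: Outcome Measure(s) notes that donation acutely lowers HbA1c by making red cells younger, so a later draw cannot stand in as a baseline for the treated arm.

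**Working it through.** **Inputs from the documents.** Effect 0.6 HbA1c points; pilot change 1130 with SD 1970; 32 per group for 80% power; 120 per arm; up to 20% dropout, so 120 × 0.8 = 96 completers per arm; Visit 2 at 7–14 days; procedures every 8 weeks; EOS 1 six months after the last phlebotomy visit.

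**Not in the documents.** The correlation r between baseline and EOS 1 HbA1c. Assumed range 0.5–0.8 for a Visit 2 value, with 0.85 also tried.

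**1. The plan's own sample size.** Standardised change = 1130/1970 = 0.574. Paired n, two-sided 5%, 80% power: ((1.960 + 0.842)/0.574)² = 23.9, so 24 (26 with the t distribution). The stated 32 gives 88% (t) to 90% (normal) power, so it is not reproduced as stated and errs on the cautious side. What matters here is that it is a paired calculation and takes no credit for the covariate. The implied SD of change is 0.6/0.574 = 1.046.

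**2. Timing.** Controls enter the EOS sequence at Visit 4, 16 weeks after Visit 2: 3.7 + 6 = about 10 months from Visit 2 to EOS 1. A treated participant who continues to Visit 6 has 32 weeks: 7.4 + 6 = about 13 months. A three-month-old value therefore lengthens an interval that is already long. (A treated participant who reaches target at Visit 3 has a shorter interval and a somewhat larger proportional penalty.)

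**3. Residual variance.** ANCOVA residual variance is proportional to 1 − r². Assume exponential decay: r(old) = R × (r/R)^((T+3)/T), with T = 10–14 months and R (reliability) = 0.9–1.0. Variance ratio V = (1 − r(old)²)/(1 − r²).

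- Example: r = 0.8, T = 10, R = 1. r(old) = 0.8^1.3 = 0.748; V = (1 − 0.560)/(1 − 0.640) = 1.22.
- r from 0.5 to 0.8: V = 1.07 to 1.22.
- r = 0.85, R = 1, T = 10–13: r(old) = 0.81–0.82; V = 1.19–1.24, an effective sample loss of 16–20% among affected participants.
- A value four months older instead of three: V up to 1.29 at r = 0.8.

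**4. Power if every participant had a three-month-old value.** Starting from exactly 80%: power = Φ(2.802/√V − 1.960).

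- V = 1.07: 77.1%. V = 1.22: 71.7%. That is about 3 to 8 points; V = 1.24 gives 71.0%.
- With no covariate, Φ(2.802 × √(1 − r²) − 1.960) = 68% at r = 0.5 and 39% at r = 0.8. The covariate thus adds 12 to 41 points, and the older value forfeits roughly 8–36% of that.
- A heavier assumption, a flat drop in r of 0.05–0.10 (which could stand for assay differences as well as age), gives 65–78%.

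**5. Power at the plan's own effect.** SD of HbA1c = 1.046/√(2(1 − r)); residual SD = that × √(1 − r²); power = Φ(effect/(residual SD × √(2/96)) − 1.960), using the flat drop of 0.05–0.10.

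| Case | Residual SD | Power, 0.6 points |
|---|---|---|
| r = 0.5 | 0.906 | 99.6% |
| r = 0.5 reduced to 0.45 | 0.934 | 99.4% |
| r = 0.8 | 0.992 | 98.7% |
| r = 0.8 reduced to 0.70 | 1.181 | 94.1% |

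The loss is about 0.2 to 5 points. At an assumed effect of 0.3 points, power goes from 55–63% to 42–61%.

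**6. Conversion outcome.** The prediabetes band is 5.7–6.4%. Its midpoint is 6.05, and the first values outside it are 5.6 and 6.5, so nobody is selected more than 0.45 points from a change of category. Drift or measurement error in one older value can produce apparent conversion.

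**The case against.** The strongest reply is that the plan loses little. Several features favour a high correlation whatever the date of the value: HbA1c integrates glucose over a red-cell lifespan of about 3.5–4 months, participants must be on stable therapy, and the cohort spans 5.7–8.5%. Only participants with a chart value are affected, and many of those values will be less than three months old. The sample size never relied on the covariate. Randomisation and a sham control keep the contrast between arms unbiased, and adjustment for baseline deals with regression to the mean in that contrast. All of this stands, and it limits the size of the point. It does not supply a baseline definition or protect the within-subject and conversion results.

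Stronger readings are tempting but not supported:

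- **That the covariate loses much of its power.** If r fell from 0.85 to 0.65–0.75, residual variance would be 1.58–2.08 times larger, a loss of 37–52% of the effective sample. Nothing in the documents gives those correlations. Under the decay model above, reaching 0.75 would need a value about 8–10 months older, and 0.65 one about 17–21 months older.
- **That chart values come from other laboratories.** This is possible, but the documents name no HbA1c laboratory for any visit, and Wake Forest recruitment draws partly on its own health system's records.
- **That a Visit 2 draw would remove the effect of weight counselling.** If Visit 2 follows screening closely, the value would reflect little of it (the interval from screening to Visit 1 is not stated). Counselling applies to both arms in any case.

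**Conclusion.** The schedule gap and the missing baseline definition are certain from the text; the size of the loss is not. On assumed correlations of 0.5–0.85 and exponential decay, a three-month-old value raises residual variance by roughly 7–24% for the participants who have one. That is about 3–8 points off 80% power if everyone were affected, and about 0.2–5 points at the plan's 0.6-point effect with 96 completers per arm. The cost would be larger only if the true effect were well below 0.6 points. A reader might infer that the primary comparison is biased; it is not, because the covariate is measured before randomisation in both arms. What remains is some lost precision, plus drift and regression to the mean in within-subject change and in the prediabetes-conversion outcome, none of which can be repaired after the first phlebotomy. This is a cheap improvement, not a threat to the trial's main conclusion.

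**What to change.** Add HbA1c to the Visit 2 draw for every participant, before the real or sham procedure, using the same laboratory or assay as EOS 1 and EOS 2. Define that value in the Statistical Plan as baseline for the primary ANCOVA, the 12-month analysis and the conversion outcome. Keep the chart or screening value for eligibility only. State in advance how a participant whose Visit 2 value falls outside the band used for selection is counted in the conversion analysis.

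For anyone already randomised without a Visit 2 value, record the date and source of the HbA1c used and run a sensitivity analysis by source. Blood is stored for research at Visit 2, but the documents do not say whether it is suitable for HbA1c.

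Cost: about 240 extra assays at a visit that already draws blood, possibly one more tube, and a short amendment to the schedule and the analysis plan.
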